3.1 General design and plan

To show the changes in the study design among protocols, the Study design is described in Table 1, and the Study design diagrams are displayed in Figure 1 and Figure 2. However, as the subject enrollment started after Protocol Amendment 1, Protocol version 1 is not included.

Forms

Title Statistical Analysis Plan Template

Code	Version	Effective Date	Page
FRM_ST03_032	01	23 Apr 2015	11 of 53

Table 1 Study Design

	Protocol Amendment 1	Protocol Amendment 2
Overall Study Design and Plan	
This Phase 2, double-blind clinical study of multiple ascending doses of KHK4083 (or placebo) with an LTE Therapy phase will be conducted in approximately 60 randomized adult subjects with moderately active UC who have a documented unsuccessful previous treatment.
 
The study will include a 4-week Screening Period, followed by a total of up to 64 weeks (treatment and follow-up) on study from the time of randomization to study completion.
 
The Treatment Period includes double-blind Induction Therapy (12 weeks) and double-blind LTE Therapy (40 weeks) for eligible subjects at Week 12.
 
Post-treatment assessments will continue for 16 weeks after the last infusion associated with the subject’s treatment period. The on-site follow-up visits will be at Weeks 16, 20, and 26 for subjects who only receive Induction Therapy or at Weeks 56, 60, and 64 for subjects who receive both Induction and LTE Therapies. The date of the subject’s last post-treatment study visit will be considered the End of Study date.
	
This Phase 2, double-blind clinical study of multiple ascending doses of KHK4083 (or placebo) with an OLE Therapy phase will be conducted in approximately 60 randomized adult subjects with moderately active UC who have a documented unsuccessful previous treatment.
 
The study will include a 4-week Screening Period, followed by a total of up to 64 weeks (treatment and follow-up) on study from the time of randomization to study completion.
 
The Treatment Period includes double-blind Induction Therapy (12 weeks) and OLE Therapy (40 weeks) for eligible subjects at Week 12. Subjects already enrolled in the double-blind, LTE under preceding versions of the protocol who worsen may be eligible to transition to the OLE up to Week 28.
 
Post-treatment assessments will continue for 16 weeks after the last infusion associated with the subject’s treatment period. The on-site follow-up visits will be at Weeks 16, 20, and 26 for subjects who only receive Induction Therapy or at Weeks 56, 60, and 64 for subjects who receive both Induction and OLE/LTE Therapies. The date of the subject’s last post-treatment study visit will be considered the End-of-Study date.

Induction Therapy: Week 0 to Week 12 (Last Dose at Week 10)	
Double-blind Induction Therapy is separated into Part A for administration of multiple ascending IV doses of KHK4083 (or placebo) to subjects in Cohorts 1 - 3 and Part B for administration of the recommended IV dose (one of three dose levels identified in Part A) of KHK4083 (or placebo) to subjects in Cohort 4. Subjects in Part A are prohibited from participating in Part B.
	
Double-blind Induction Therapy is separated into Part A for administration of multiple ascending IV doses of KHK4083 (or placebo) to subjects in Cohorts 1 - 3 and Part B for administration of the recommended IV dose (one of three dose levels identified in Part A) of KHK4083 (or placebo) to subjects in Cohort 4. Subjects in Part A are prohibited from participating in Part B.

Forms

Title Statistical Analysis Plan Template

Code	Version	Effective Date	Page
FRM_ST03_032	01	23 Apr 2015	12 of 53

	Protocol Amendment 1	Protocol Amendment 2
Long-term Extension Therapy: Week 12 (First Dose) to Week 52	
Subjects who complete double-blind Induction Therapy (i.e., at least five of six treatments) and have a clinical response or mucosal healing are eligible to continue in double-blind LTE Therapy
 
All subjects who qualify will be given two options: 1) To receive no further treatment and proceed directly to the Induction Therapy Follow-up Period (Week 16 through Week 26); or 2) To continue in double-blind LTE Therapy and receive 10 additional treatments of KHK4083 (at the same dose administered to that subject during Induction Therapy) or placebo as maintenance therapy. Each subject will receive one IV infusion every 4 weeks from Week 12 to Week 48 followed by an End-of-LTE Therapy visit at Week 52, and then proceed to the LTE Therapy Follow-up Period (Week 56 through Week 64). Refer to Section 8.1.4.2 for additional dosing details in LTE Therapy.
 
All other subjects, including those who do not complete double-blind Induction Therapy (non-completers), do not meet the criteria for a clinical response, or do not have mucosal healing at Week 12 will receive no further treatment, and thus enter the Induction Therapy Follow-up Period.
	
The LTE is only active for subjects who entered it prior to approval of Amendment 2. Subjects who sign an ICF under Amendment 2 are eligible for the OLE. Subjects who completed double-blind Induction Therapy (i.e., at least five of six treatments) and had a clinical response or mucosal healing were eligible to continue in double-blind LTE Therapy.
 
All subjects who qualified were to have been given two options: 1) To receive no further treatment and proceed directly to the Induction Therapy Follow-up Period (Week 16 through Week 26); or 2) To continue in double-blind LTE Therapy and receive 10 additional treatments of KHK4083 (at the same dose administered to that subject during Induction Therapy) or placebo as maintenance therapy. Each subject will receive one IV infusion every 4 weeks from Week 12 to Week 48 followed by an End-of-LTE Therapy visit at Week 52, and then proceed to the LTE Therapy Follow-up Period (Week 56 through Week 64).
 
Note: Subjects who already started treatment in the double-blind LTE Therapy will continue to receive KHK4083 or placebo during LTE Therapy. If their UC worsens or flares up to Week 28, they may transition to OLE therapy.
 
Subjects who did not qualify were to have received no further treatment and entered the Induction Therapy Follow-up Period.


Forms

Title Statistical Analysis Plan Template

Code

Version

Effective Date

Page

FRM_ST03_032

01

23 Apr 2015

13 of 53

	Protocol Amendment 1	Protocol Amendment 2
Open-label Extension Therapy: Week 12 (First Dose) to Week 52		
Subjects who complete double-blind Induction Therapy (i.e., at least five of six treatments) are eligible to enter OLE Therapy (refer to Section 7.4 for specific eligibility criteria). All subjects who qualify will be given two options:
 
1) To receive no further treatment and proceed directly to the Induction Therapy Follow-up Period (Week 16 through Week 26); or
 
2) To receive 10 treatments of open-label KHK4083 (at the same dose administered to that subject during Induction Therapy) as maintenance therapy. Each subject will receive one IV infusion every 4 weeks from Week 12 to Week 48 followed by an End-of-OLE Therapy visit at Week 52, and then proceed to the OLE Therapy Follow-up Period (Week 56 through Week 64).
 
Subjects participating in the double-blind LTE who experience a clinical worsening or a flare of disease up to Week 28, as defined by the Investigator, may transition to the OLE.
 
Subjects will maintain the same visit schedule, e.g., a subject who completed a Week 20 visit in the LTE and transitions to the OLE at Week 24 will have an OLE Week 24 visit. However, for the first two open-label doses in the OLE, additional safety monitoring will include ECGs and post-infusion monitoring as performed for the OLE Week 12 and Week 16 visits, respectively.

[figure not shown]
	Forms			
	Title	Statistical Analysis Plan Template		
	Code	Version	Effective Date	Page
	FRM_ST03_032	01	23 Apr 2015	14 of 53

Figure 1 Study Design Diagram in Protocol Amendment 1

NC or NR Non-completer (NC) – Subject did not complete Induction Therapy; or Non-responder (NR) – Subject did not meet the criteria of a clinical response at Week 12.

R Randomization to double-blind Induction Therapy.

- a: Subjects will be in the study for a total of up to 64 weeks from the time of randomization to study completion. The double-blind Treatment Period includes Induction Therapy (12 weeks) and Long-term Extension (LTE) Therapy (40 weeks). A post-treatment Follow-up Period will be conducted either at Weeks 16, 20, and 26 for subjects who only receive Induction Therapy or at Weeks 56, 60, and 64 for subjects who receive both Induction and LTE Therapies.
- b: Cohort 4 will receive the recommended dose (1.0, 3.0 or 10 mg/kg) determined from safety assessments of Cohorts 1 - 3 in Part A.
- c: Subjects who complete Induction Therapy, have evaluable total Mayo Clinic scores, and have met the criteria for a clinical response or mucosal healing will have the option to continue in LTE Therapy. Subjects who qualify will receive 10 additional treatments (one IV infusion every 4 weeks) of KHK4083 (at the same dose administered to that subject during Induction Therapy) or placebo. (Note: Subjects administered placebo during Induction Therapy will receive placebo during LTE Therapy).
- C=cohort; LTE=long-term extension; MAD= multiple ascending dose.

[figure not shown]
	Forms			
	Title	Statistical Analysis Plan Template		
	Code	Version	Effective Date	Page
	FRM_ST03_032	01	23 Apr 2015	15 of 53

Figure 2 Study Design Diagram in Protocol Amendment 2

Non-completer (NC) - Subject did not complete Induction Therapy

- a: **For those subjects who enrolled under Amendment #1-** Subjects will be in the study for a total of up to 64 weeks. The double blind treatment period includes Induction Therapy (12 weeks) and LTE therapy (40 weeks). A post treatment follow-up period will be conducted at either Weeks 16, 20 and 26 for subjects who only receive Induction Therapy or at weeks 56, 60 and 64 for subjects who receive both induction and LTE Therapies
- b: Cohort 4 will receive the recommended dose (1.0, 3.0, or 10 mg/kg) determined from safety assessments of Cohorts 1 - 3 in Part A.
- c: Endoscopic Responders (ER) include subjects who met the criteria for clinical response at Week 12 and non-responders (NR) includes subjects who did not meet the criteria of a clinical response at Week 12.
- d: **For those subjects who enroll under Amendment #2-**All subjects who complete the induction period, i.e., (received at least of 5 of the 6 doses of double-blind therapy and have Week 12 sigmoidoscopy results from the central reader) and are eligible to continue on in the study have the option to enter the OLE therapy part of the trial and receive 10 additional treatments of KHK4083 once every 4 weeks from week 12 through week 48 at the same dose used in the cohort that they were enrolled in.

C=cohort; IV=intravenous; LTE=long-term extension; OLE=Open-label Extension; MAD=multiple ascending dose; R=randomization.

	Forms			
	Title	Statistical Analysis Plan Template		
	Code	Version	Effective Date	Page
	FRM_ST03_032	01	23 Apr 2015	16 of 53

3.2 Sample size justification

Assuming a 15% dropout rate, it is anticipated that approximately 60 subjects will be required to be randomized in order to achieve 51 evaluable subjects in the full analysis set (FAS). In Part A (Cohorts 1 - 3), the sample size is based on the feasibility of the safety and tolerability assessment to recommend starting the treatment of the next cohort of 12 subjects/cohort (9 subjects to receive KHK4083 and 3 subjects to receive placebo). In Part B (Cohort 4) for the treatment of 24 subjects (18 subjects to receive KHK4083 at the recommended dose based on the safety and tolerability in Part A and 6 subjects to receive placebo), the sample size is based on the feasibility of exploratory assessments in efficacy and safety at the recommended dose level. Based on the UCEIS and Mayo Clinic scores and from combining Part A and Part B, it is planned to have approximately a total of 27 randomized subjects receive the recommended dose of KHK4083 and 15 subjects receive placebo.

3.3 Randomization and blinding

After a subject meets all study eligibility requirements at Screening, the Interactive Response Technology (IRT) system will be used by the Investigator (or designee) to randomize the subject to double-blind Induction Therapy on Day 1 (Week 0). Subjects randomly assigned in Cohorts 1 - 3 will receive either KHK4083 (one of three dose levels) or placebo in a 3:1 ratio during Part A of Induction Therapy. Additional subjects (Cohort 4) in a 3:1 ratio will receive the recommended KHK4083 dose or placebo during Part B of Induction Therapy.

The subject, Investigator (or investigative site personnel) and KHK4083 study team at KKD will not know the treatment to which the subject is randomized during the double-blind Treatment Period. Placebo will be administered by IV infusion to each cohort to ensure blinded treatment. The study is being blinded to prevent bias in the safety evaluation, in particular the severity grading and causality determinations of AEs. However, at any time during the study, if a medical emergency occurs and subject treatment must be known, the blind may be broken according to the procedure described in protocol.

3.4 Efficacy endpoints

3.4.1 Primary endpoint

Subjects with moderately active UC will primarily be evaluated for an improvement in the mucosa determined by their mMES (subscores from 0 to 3, with modified endoscopy finding scoring, i.e., by excluding mild friability from a subscore of 1) at completion of double-blind Induction Therapy. The primary efficacy endpoint will be the mean change in the mMES from Baseline (Week 0) to Week 12 for all subjects who receive the recommended dose in Parts A and B.

	Forms			
	Title	Statistical Analysis Plan Template		
	Code	Version	Effective Date	Page
	FRM_ST03_032	01	23 Apr 2015	17 of 53

3.4.2 Secondary efficacy endpoints

The secondary efficacy endpoints for all subjects who receive the recommended dose during double-blind Induction Therapy are as follows:

- Improvement in the mucosa at Week 12;
 - Changes in the mucosa will be based on the percentage of subjects with at least a 1-point improvement in their mMES (0 to 3) from Baseline (Week 0) to Week 12; and/or
 - Changes in the mucosa will be based on the percentage of subjects with at least a 1-point improvement in their modified Baron endoscopic score (5-point scale) from Baseline (Week 0) to Week 12; and/or
 - Changes in the mucosa will be based on the mean change in UCEIS (0 to 8) and subscores from Baseline (Week 0) to Week 12.
- Mucosal healing at Week 12;
Mucosal healing is defined as a mMES of 0 or 1.
- Clinical improvement at Week 12;
Improvement will be based on a reduction (mean change from Baseline [Week 0] at Week 12) in the total Mayo Clinic score (0 to 12).
- Clinical improvement at Weeks 2, 4, 6, 8, 10, and 12;
Improvement will be based on mean changes from Baseline (Week 0) in the partial (excludes endoscopy subscores) Mayo Clinic score (0 to 10).
- Clinical response at Week 12;
A clinical response is defined as a reduction in the total Mayo Clinic score of at least 3 points and a decrease of at least 30% from Baseline (Week 0) to Week 12, and a reduction in the rectal bleeding subscale of at least 1 point from Baseline (Week 0) to Week 12 or an absolute rectal bleeding score of 0 or 1 at Week 12.
- Clinical remission at Week 12;
Clinical remission is defined as a total Mayo Clinic score of ≤ 2 and no subscores > 1 .

For all subjects who receive KHK4083 at dose levels different than the recommended dose during double-blind Induction Therapy, improvement in the mucosa at Week 12 based on the mean change in the mMES from Baseline (Week 0) to Week 12 is the main secondary endpoint. The other secondary efficacy endpoints at Week 12 for all subjects who receive KHK4083 at other than the recommended dose are the same as those listed and defined above, i.e., improvement in the mucosa based on the modified Baron endoscopic score and the UCEIS; mucosal healing; clinical improvement based on total, as well as partial (excludes endoscopy subscore at Weeks 2, 4, 6, 8, 10, and 12) Mayo Clinic scores; clinical response; and clinical remission.

3.4.3 Exploratory efficacy endpoints

	Forms			
	Title	Statistical Analysis Plan Template		
	Code	Version	Effective Date	Page
	FRM_ST03_032	01	23 Apr 2015	18 of 53

Efficacy exploratory endpoints will be included in this study for all subjects with moderately active UC who receive both Induction Therapy and OLE/LTE Therapy. The exploratory endpoints for all subjects who receive both Induction Therapy and OLE/LTE Therapy are as follows:

- Clinical improvement at Week 52;
Improvement will be based on a reduction (mean change from Baseline [Week 0] to Week 52) in the total Mayo Clinic score (0 to 12).
- Clinical improvement at Weeks 16, 20, 24, 28, 32, 36, 40, 44, 48, and 52 and at OLE/LTE Therapy Follow-up Period visits (Weeks 56, 60, and 64);
Improvement will be based on mean changes from Baseline (Week 0) in the partial (excludes endoscopy subscores) Mayo Clinic score (0 to 10).
- Clinical response at Week 52;
A clinical response is defined as a reduction in the total Mayo Clinic score of at least 3 points and a decrease of at least 30% from Baseline (Week 0) to Week 52, and a reduction in the rectal bleeding subscale of at least 1 point from Baseline (Week 0) to Week 52 or an absolute rectal bleeding score of 0 or 1 at Week 52.
- Clinical remission (i.e., a total Mayo Clinic score of ≤ 2 and no subscores > 1) at Week 52;
- Durable clinical responses and durable clinical remissions at Week 52 (i.e., present at both Week 12 and Week 52), and glucocorticoid-free clinical remission at Week 52;
- Mucosal healing (i.e., an mMES of 0 or 1) at Week 52;
- Improvement in the mucosa according to the following assessments:
 - At least a 1-point improvement in the mMES from Baseline (Week 0) to Week 52;
 - A mean change in the UCEIS score from Baseline (Week 0) to Week 52; and/or
 - At least a 1-point improvement in the modified Baron endoscopic score from Baseline (Week 0) to Week 52.
- Remission (i.e., mMES of 0 or 1, stool frequency subscore of 0 or 1, and rectal bleeding subscore of 0) rates at Week 12 and Week 52;
- Improvement in the HRQL, which will be based on the subject's completed IBDQs;
- Lowered corticosteroid (glucocorticoid) dosages;
- Glucocorticoid-free treatment duration from Week 16 through Week 52, and through the OLE/LTE Therapy Follow-up Period (Week 56 through Week 64);

3.5 Safety endpoints

The safety and tolerability of KHK4083 will be determined by physical examination, vital signs, body weight, 12-lead ECGs, and clinical laboratory findings; and the number and percentage of subjects reporting AEs (frequency, severity, and relationship to investigational product), SAEs, and treatment discontinuation due to AEs.

3.6 Other endpoints

	Forms			
	Title	Statistical Analysis Plan Template		
	Code	Version	Effective Date	Page
	FRM_ST03_032	01	23 Apr 2015	19 of 53

- PD profile of KHK4083
- PK-PD relationships

The analysis of PK, PD and immunogenicity data and parameters corresponding to those data are beyond the scope of this SAP. Separate analysis plans may be developed for these analyses.

4. Statistical Analysis

4.1 General

General descriptive statistics for continuous variables include the n (number of observed values), the mean, standard deviation, median, minimum, and maximum values. For categorical variables, the number and percentage of subjects with a specific level of the variable will be presented. The percentage will be calculated using the subjects with a reported value. Counts of missing subjects will be identified for variables that had one or more subjects with a missing result. Descriptive statistics will be presented by treatment Cohort (KHK4083 dose levels; combined KHK4083; and placebo) and by visit.

Unless there are any notes, the following rules will be applied for all tables and figures;

- Data from placebo subjects in each Cohort will be combined, not depending on treatment period (Double-Blind Induction Therapy, Long-Term Extension Therapy, Open-Label Extension Therapy, or Follow-up).
- In the case that Screening or Baseline is necessary in the tables and figures related to LTE Therapy Period, OLE Therapy Period, or Follow-up Period, the data at Screening or Baseline will be used or displayed.
- Double-Blind Therapy Period will be defined as the period including both Double-Blind Induction Therapy Period and LTE Therapy Period.
- When “Week xx” (xx: number) is necessary, “Week xx” displayed on CRF will be used or displayed.

To explain how data are summarized, the figure showing the relationship between period and dose of Investigational Product is displayed in Figure 3 and the table defining the category is displayed in Table 2.

[figure not shown]
	Forms			
	Title	Statistical Analysis Plan Template		
	Code	Version	Effective Date	Page
	FRM_ST03_032	01	23 Apr 2015	20 of 53

Figure 3 Relationship between Period and Dose of Investigational Product

Subjects who do not move to OLE/LTE Therapy

Subjects who move to OLE/LTE Therapy

[figure not shown]

Table 2 Category in Tables and Figures

	4083 Randomized				Placebo Randomized			
	Cohort 1	Cohort 2	Cohort 3	Cohort 4	Cohort 1	Cohort 2	Cohort 3	Cohort 4
Summary Pattern	Category In Tables and Figures							
Double-Blind Induction Therapy Period	1.0 mg/kg	3.0 mg/kg	10 mg/kg	1.0, 3.0 or 10 mg/kg	Placebo			
Double-Blind Therapy Period ¹⁾								
Double-Blind Therapy Period and Double-Blind Therapy Follow-up Period ²⁾								
LTE Therapy Period								
LTE Therapy Period and Double-Blind Therapy Follow-up Period	1.0 mg/kg	3.0 mg/kg	10 mg/kg	1.0, 3.0 or 10 mg/kg	Placebo ³⁾			
OLE Therapy Period								
OLE Therapy Period and OLE Therapy Follow-up Period								

1) Double-Blind Therapy Period includes both Double-Blind Induction Therapy Period and LTE Therapy Period.

2) Double-Blind Therapy Follow-up Period includes both Follow-up Periods after Double-Blind Therapy Period and LTE Therapy Period.

3) For subjects randomized to Placebo, they receive 4083 administration during the duration but they are summarized as one category as "Placebo".

Image which shows the relationship between summary pattern and data will be displayed in Figure 4.

Figure 4 Summary Patterns

Forms

Title Statistical Analysis Plan Template

Code

Version

Effective Date

[figure not shown]
Page

FRM_ST03_032

01

23 Apr 2015

21 of 53

General reporting conventions will include the following:

- The baseline value for any measurement is the last value obtained prior to receiving administration of KHK4083 or placebo on Day 1 at Week 0. All nominal time points will be used for analysis; actual assessment times will not be used to reclassify the time point at which a measure was taken.

	Forms			
	Title	Statistical Analysis Plan Template		
	Code	Version	Effective Date	Page
	FRM_ST03_032	01	23 Apr 2015	22 of 53

- Study day: Study day will be calculated relative to the date of KHK4083 or placebo administration (Day 1) as:
 - (If Date of event \geq Date of first investigational product administration) Date of event – Date of first investigational product administration + 1 and
 - (If Date of event $<$ Date of first investigational product administration) Date of event – Date of first investigational product administration

This formula will be used when calculating days to a specific event (i.e., concomitant medication and/or AE start date). A negative study day indicates an event prior to investigational product administration.

- Unless otherwise noted, all percentages will be presented to one decimal place.
- Individual data listings of all data represented on the eCRF will be provided as an appendix to facilitate investigation of the tabulated values and to allow for the clinical review of all variables. All data listings will be sorted by dose Cohort, site-subject number, visit, and time points where appropriate.
- Post-dose data from unscheduled visits will be excluded from the summary tables but included in the data listings.

Statistical hypothetical testing will not be carried in this study. However, in the case that p-value is derived, it will be rounded to three decimal places.

All statistical analyses will be performed using Statistical Analysis System (SAS) statistical software (Version 9.2 or higher). AEs will be coded for summarization using Medical Dictionary for Regulatory Activities (MedDRA® Version 18.1). Concomitant medications will be coded using WHO Drug Dictionary (enhanced) 1st Q2015 B-format.

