	Title	Statistical Analysis Plan Template		
	Code	Version	Effective Date	Page
	FRM_ST03_032	01	23 Apr 2015	7 of 53

Revision History

Document Version	Changes Made	Document Date
Version Draft 1.0	First draft based on Protocol draft 4083-002, dated 07 July 2015 and Final CRF, dated 23 Nov 2015.	31 Mar 2016
Version Draft 2.0	Second draft based on Protocol 4083-002 Amendment 1, dated 15 Oct 2015 and Final CRF, dated 23 Nov 2015.	08 Apr 2016
Version Draft 3.0	Third draft based on Sponsor revision of draft version 2.0	12 May 2016
Version Draft 4.0	Third draft based on Sponsor revision of draft version 3.0	25 Oct 2016
Version 1		09 Dec 2016
Version 2	Amended for denominator changes, TLF list changes, and unblinding at Week 12.	06 Oct 2017

	Forms			
	Title	Statistical Analysis Plan Template		
	Code	Version	Effective Date	Page
	FRM_ST03_032	01	23 Apr 2015	8 of 53

1. Introduction

Ulcerative colitis (UC) is considered as one of the common gastrointestinal autoimmune diseases, and is referred to as immune-mediated inflammatory disease. KHK4083 is a fully human, non-fucosylated IgG1 monoclonal antibody (mAb) specific for the costimulatory molecule OX40, a tumor necrosis factor receptor (TNFR) family member. KHK4083 binds with high affinity and specificity to an extracellular domain epitope of OX40, which plays a key role in maintaining late T-cell proliferation and survival by suppressing apoptosis, and in inducing T-cell memory formation.

This study will determine the safety and tolerability of administration of multiple ascending doses of KHK4083, and determine if the recommended dose of KHK4083 improves the mucosa in subjects with moderately active UC.

This statistical analysis plan (SAP) describes the statistical analysis and summary to be performed for the study described in Protocol 4083-002 Amendment 2, dated 04 Oct 2016 and titled:

“A Phase 2, Multicenter, Randomized, Double-blind, Placebo-controlled Multiple Ascending Dose Study (Induction Therapy and Long-term Extension Therapy) of an Anti-OX40 Monoclonal Antibody (KHK4083) in Subjects with Moderately Active Ulcerative Colitis”

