4.4 Handling of missing and incomplete data

Available data at each time point will be presented. The denominator for percentages will be based on the number of subjects in the appropriate treatment or cohort group for summary purposes.

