9.2 Programming conventions

All tables/listings will be presented in landscape format.

The standard font size is 9 points Courier New for all tables. Listings will be presented with an 8 or 7 points Courier New.

Titles will be center-aligned; footnotes will be left-aligned.

Each table/figure/listing will have 2 titles:

- The 1st title will be the table/figure/listing number with the description of the table/figure /listing;
- The 2nd title will be a description of the study population presented in the table/figure/listing. Some tables will have another title (before 2nd title) with a description of the statistical method used in those tables.

Any footnote added to explain the table/listing/figure contents will be presented in the following format:

Note 1: Percentages are calculated on the number of subjects (N).

Note 2: A serious adverse event is an....

Note 3:

The last two footnotes of each table/figure will be footers indicating:

- the reference listing of the data;
- the program name, the date and time of generation and the SAS[®] version used.

The last footnote of each listing will be a footer indicating the program name, the date and time of generation and the SAS[®] version used.

	Forms			
	Title	Statistical Analysis Plan Template		
	Code	Version	Effective Date	Page
	FRM_ST03_032	01	23 Apr 2015	38 of 53

In the tables and listing the treatment under comparison will be labeled as “Cohort 1 1.0 mg/kg”, ‘Cohort 2 3.0 mg/kg’ “Cohort 3 10 mg/kg”, ‘Cohort 4 XX mg/kg’ (XX is the recommended dose) and “Placebo”.

In tables and figures, unless otherwise stated, the number of subjects corresponding to analysis set will be shown at the part of “N=XX” together with the labels of treatment group.

- For example, in Table 14.3.1-1.1 “Overall summary of treatment-emergent adverse events during study / safety analysis set”, the part of “N=XX” will display the number of subjects in safety analysis set corresponding to the labels of the treatment group (e.g. 1.0 mg/kg, 3.0 mg/kg, 10 mg/kg, Placebo) and All.

Unless otherwise stated, listings will be presented by randomized treatment, and sorted by cohort and the site-subject identifier.

Except for the listings 16.2.1-1.2 (based on screening failure subjects) and 16.2.1-1 (based on all subjects), all the listings will be based on the randomized subjects.

In all the listings on safety variables, a column with a flag (§) for treatment misallocation will identify the treatment misallocations.

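### SAP 4.1 and 4.4 set different percentage divisors with no precedence rule, and the open-label adverse-event tables are titled on a Safety Set that includes subjects never dosed in that period

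*SAP*

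**What the plan says.** On the divisor, SAP 4.1 states "The percentage will be calculated using the subjects with a reported value" and has missing subjects counted separately. SAP 4.4, the missing-data section, first says that available data will be presented at each time point and then states "The denominator for percentages will be based on the number of subjects in the appropriate treatment or cohort group for summary purposes". A sample footnote in SAP 9.2 puts percentages on N, but it is there to show footnote format. The Version 2 entry in the SAP revision history reads "Amended for denominator changes, TLF list changes, and unblinding at Week 12"; it does not say which text was changed or which prevails.

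On N, SAP 9.2 says that, unless otherwise stated, "the number of subjects corresponding to analysis set will be shown at the part of" the column header that carries N. Neither analysis set in SAP 4.2 is period-specific. The Safety Analysis Set is everyone given any investigational product. The Full Analysis Set (FAS) needs one full dose, Baseline data and a post-treatment value of the primary variable. The six OLE adverse-event tables (14.3.1-1.4, -2.3, -2.6, -3.3, -4.3 and -5.3) carry the Safety Set in their titles, and the OLE Week 52 response table (14.2-3.7) carries the FAS.

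OLE entry is conditional: "Subjects who complete double-blind Induction Therapy (i.e., at least five of six treatments) are eligible to enter OLE Therapy" (SAP 3.1, Table 1). It is also optional, since a qualifying subject may choose no further treatment. SAP 3.4.3 limits the exploratory efficacy endpoints to subjects who receive both Induction and OLE or long-term extension (LTE) therapy. For the double-blind tables, SAP 4.1 adds "Double-Blind Therapy Period will be defined as the period including both Double-Blind Induction Therapy Period and LTE Therapy Period".

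**The concern.** Two programmers who both follow the SAP could report different response rates from the same data, one dividing by subjects with a value and the other by everyone in the group.

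The OLE tables raise a second problem. The Safety Set includes subjects who could have no OLE event because they had no OLE dose. These are subjects who declined further treatment, had fewer than five induction infusions, failed to qualify for the LTE under Amendment 1, or stayed in the blinded LTE. SAP 8.1 assigns events to periods but gives no matching count of subjects at risk. If these subjects remain in N, OLE incidence is diluted. This matters most for placebo-randomized subjects: SAP Table 2 (note 3) keeps them under a Placebo label in the OLE, although that is their first exposure to KHK4083.

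**Working it through.** **Inputs from the documents.** SAP 3.2 gives 60 randomized, 51 in the FAS, 15% dropout, 27 on the recommended dose and 15 on placebo. Each of the other two dose levels has 9 (Protocol 8.1.4.1). The documents give no OLE entry, event or Week 52 assessment counts, so those below are assumptions.

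**The plan's own figures.** 51/(1 − 0.15) = 60, as stated. The arms add up: 27 + 15 + 9 + 9 = 60. FAS in the recommended-dose arm: 27 × 0.85 = 22.95, taken as 23.

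**Step 1: SAP 4.1 against 4.4 at Week 12.** Assume 8 clinical responders.
- No value missing: 8/23 = 34.8% under both rules.
- Two subjects without a total Mayo score: 8/23 = 34.8% under 4.4, 8/21 = 38.1% under 4.1.

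Percentages based on the endoscopy subscore hardly move, because FAS entry already requires a post-treatment value of that score.

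**Step 2: OLE adverse events.** Percentage as titled = x / (Safety Set N). Percentage among those at risk = x / (OLE-dosed). The first equals the second multiplied by (OLE-dosed)/(Safety Set N).

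| Group | Subjects with event | On Safety Set | OLE-dosed (assumed) | On OLE-dosed | Factor |
|---|---|---|---|---|---|
| Recommended dose | 3 | 3/27 = 11.1% | 24 | 3/24 = 12.5% | 24/27 = 0.89 |
| Recommended dose | 3 | 3/27 = 11.1% | 22 | 3/22 = 13.6% | 22/27 = 0.81 |
| Recommended dose | 3 | 3/27 = 11.1% | 16 | 3/16 = 18.8% | 16/27 = 0.59 |
| Placebo-randomized | 2 | 2/15 = 13.3% | 10 | 2/10 = 20.0% | 10/15 = 0.67 |
| Nine-subject dose arm | 1 | 1/9 = 11.1% | 6 | 1/6 = 16.7% | 6/9 = 0.67 |

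Because the factor depends on each group's entry share, comparisons between groups can shift too. With 22 of 27 and 10 of 15 entering, the difference between placebo-randomized and recommended-dose subjects is 13.3 − 11.1 = 2.2 points on the Safety Set and 20.0 − 13.6 = 6.4 points on OLE-dosed subjects.

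**Step 3: Week 52 response.** SAP 3.4.3 already removes induction-only subjects, so the remaining difference is between subjects dosed in the period and subjects assessed. For Table 14.2-3.7, assume 6 responders:
- 20 dosed, 18 assessed: 6/20 = 30.0% against 6/18 = 33.3%.
- 16 dosed, 13 assessed: 6/16 = 37.5% against 6/13 = 46.2%.

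For Table 14.2-3.6, the Double-Blind Therapy Period includes Induction, so a FAS title fits the period. Only subjects who stay in the LTE can have a double-blind Week 52 value, however, so 4.1 and 4.4 still give different rates. The documents do not support a usable LTE count, so no figure is offered.

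**The case against.** **The two rules can be read together.** SAP 4.4 opens with available data, and Protocol 12.6 treats missing values as missing. On that reading, 4.4 only says that percentages are taken within the right group. This is fair as far as it goes, but both texts say that nothing is imputed; neither sets the divisor.

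**N may be defined elsewhere.** SAP Figures 3 and 4 are there to explain how data are summarized by period, and the shells are a separate document (SAP 9.7). None could be examined here. SAP 9.2 allows exceptions, and its worked example is a whole-study table for which the full Safety Set is right. The title suffix may name only the parent set, and *appropriate* in 4.4 may mean subjects in the period. This stands, and it makes the OLE part conditional.

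**Week 52 efficacy is already restricted.** This stands. A reader might infer from the FAS titles that induction-only subjects must be counted in the OLE Week 52 rate; SAP 3.4.3 says otherwise. What remains is that the titles do not reflect that limit and that 3.4.3 does not separate OLE from LTE.

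**The stakes are low.** All analyses are descriptive or exploratory (Protocol 12.3.5), and the proof-of-concept decision uses 12-week data (SAP 4.5). Disposition by period (SAP 5.1) and OLE exposure (Table 14.1-7) should let a reader rescale the rates. This stands as a limit on severity, though a safety table should not need rescaling.

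**Dividing by assessed subjects has its own bias.** LTE subjects who flare may move to the OLE and then have no double-blind Week 52 value, so an assessed-only rate drops treatment failures. This stands, and the fix allows for it.

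**Conclusion.** The concern holds in two parts. First, SAP 4.1 and 4.4 conflict whenever a value is missing, and no text gives precedence. A reader might take the Version 2 note or the 9.2 footnote as settling it for 4.4. The note does not say what changed, and the footnote is a format example.

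Second, on the text available, the six OLE adverse-event tables default to a Safety Set N that includes subjects never dosed in the OLE. If neither the figures nor the shells override this, the percentages are multiplied by (OLE-dosed)/(Safety Set N): 0.59 to 0.89 in the recommended-dose illustrations and 0.67 in the placebo-randomized one. These sizes rest wholly on assumed entry and event counts and on planned arm sizes.

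The documents do not support saying that understatement is certain, or that the Week 12 conclusions are at risk. The primary ANCOVA is unaffected and Week 12 responder rates change little. This is a minor to moderate clarification of reporting.

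**What to change.** 1. **One rule.** Make SAP 4.1, 4.4 and 9.2 state the same divisor. In responder tables, show the number missing and give both the rate on subjects with a reported value and the rate on N, naming one as the lead.
2. **OLE safety tables.** For all six OLE adverse-event tables, and likewise the OLE concomitant-medication table (14.1-3.4) and the OLE QTcF percentage tables, set N to Safety Set subjects with at least one OLE dose, by SAP Table 2 category.
3. **Week 52 tables.** Set N to FAS subjects dosed in that period. In Table 14.2-3.6, keep subjects who moved from LTE to OLE in the LTE N, show them on their own line as having no double-blind Week 52 value, and do not present the assessed-only rate alone.

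If the shells already define these divisors, bring that wording into the SAP and remove the conflict between 4.1 and 4.4.

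The cost is wording, titles and footnotes, with no new data: OLE dosing dates are already used in SAP 6.1 and moves from LTE to OLE are already counted under SAP 5.1. The downside is that some OLE adverse-event rates will read higher and responder tables will carry a second rate.
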